A 22-question questionnaire will be sent to the eligible candidates (see NCT05900791 and NCT05845177). The questionnaire is developed by combining domains from previously validated Patient Reported Outcome Measures (PROMs). Five questions are taken from the Western Ontario and McMaster Universities Osteoarthritis Index (WOMAC) pain domain; seven questions from the Douleur Neuropathique 4 interview (DN4i); a numerical rating scale (NRS) question for pain in the operated joint in the last week; satisfaction; a single question for each of the following: willingness to repeat the surgery; pain frequency; pain interference with daily activities; other chronic pain conditions; patient-reported use of analgesics; weight; height and the permission to contact respondents again later. Patient reported weight and height has been recently found valid in a Danish e-survey setting.¹⁸ A detailed description of the questionnaires and the current validation status of the domains can be found in 2 different papers.^{19,20} The Danish and an English version of the questionnaire will be available in the final publication.

Sample characteristics

Patients with THA and knee arthroplasty who received their arthroplasty 11-15 months prior to the intended date of survey administration will be identified based on the NOMESCO (Nordic Medico-Statistical Committee) Classification of Surgical Procedures from the the Danish National Patient Register by using SKS-code. The codes for THA patients will be SKS-code DM16 [hip osteoarthritis] + KNFB20 or KNFB30 or KNFB40[Primary Total Hip Arthroplasty]. For total knee arthroplasty (TKA), SKS-code DM17 [knee osteoarthritis] + KNGB20, KNGB30 or KNGB40 [primary total knee arthroplasty]). For medial unicompartmental knee arthroplasty (UKA), SKS-code DM17 [knee osteoarthritis] + KNGB01 or KNGB11 [primary medial unicompartmental knee arthroplasty]. The baseline characteristics of the sample including their BMI will be gathered from the Danish Hip Arthroplasty Register (DHR) and the Danish Knee Arthroplasty Register (DKR).

Survey administration

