The data of this study is pooled from 2 surveys sent to THA and knee arthroplasty patients.^{19,20} Both surveys are distributed via 'Digital Post' which is linked to the unique Civil Registration number (CPR) using Research Electronic Data Capture (REDCap) software (www.r-project.org). A reminder will be sent 14 days after distribution for non-responders. A month after distribution date, a text-message will be sent to non-responder's telephone number if it is registered in the electronic patient file.

Statistical analysis

We expect to find a sample of around 6400 patients divided between hip and knee arthroplasty. Estimated response rates of 70% will leave us with 2240 patients to be analysed in each joint arthroplasty group. With an expected 15% of the sample to be weight gainers, we will be able to detect a minimum of 16.6% difference in the incidence of the outcome between gainers and non-gainers with a significance level of 0.05 with a power of 0.80.

We will report results for THA, TKA and medial UKA separately as we believe these are different patient groups. We will categorize patients into weight gainers ($\geq 5\%$ weight gain after arthroplasty), weight losers ($\geq 5\%$ weight loss) and those who maintain their weight. Descriptive statistics of the baseline characteristics of the three categories with the following variables will be presented in table 1: age, sex, BMI and surgical details (type of anaesthesia, operation length, use of local infiltration analgesia (LIA), use of cement, and surgical complications).

The primary outcome is the occurrence of PPP and will be defined as NRS pain score higher than 3 as proposed by Moore et. al.²¹ Secondary outcomes include satisfaction defined as being very satisfied or

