satisfied; willingness to repeat the surgery defined as answering “yes” in willingness question; frequent pain defined as experiencing pain constantly, daily or few times a week; use of analgesic; interference with daily activities, defined as answering “some”, “much” and “very much”; WOMAC pain score will be reported as the mean (standard deviation [SD]). Following outcome dichotomization (except for WOMAC pain), we will employ a multivariate logistic regression model to estimate the Odds Ratio (OR) and the corresponding 95% Confidence Interval (CI) amongst gainers and losers in relation to those who maintained their weight. For WOMAC pain, we will report the mean difference (MD) and the corresponding 95% CI. We will stratify for baseline obesity status (non-obese: $BMI < 30 \text{ kg/m}^2$, Obese: $BMI \geq 30 \text{ kg/m}^2$). We will run a non-adjusted analysis first, then we will adjust for age, sex and the use of cement. We will do a sensitivity analysis to see whether the effect size is different between non-morbidly obese ($BMI 30-39 \text{ kg/m}^2$) and morbidly obese ($BMI \geq 40 \text{ kg/m}^2$), we will run another sensitivity analysis adjusting for patients having other chronic pain condition. Data is handled in the most recent version of R (www.r-project.org).

Table 1 (Demographics)

	THA			TKA			Medial UKA		
Demographics	Weight gainers	Weight losers	Weight unchanged	Weight gainers	Weight losers	Weight unchanged	Weight gainers	Weight losers	Weight unchanged
Total N									
Age (mean)									
Female N (%)									
BMI (mean)									
General Anaesthesia N (%)									
Spinal Anaesthesia N (%)									
Operation time (mean)									

Use of Cement N (%)									
Local Infiltration of analgesia N (%)									
Surgical complication N (%)									

Table 2 (Risk of developing PPP)

	Weight unchanged (Reference group)				Weight gainers					Weight losers				
	N	PPP: N (%)	OR (95% CI)	P value	N	PPP: N (%)	OR (95% CI)	Adjusted OR (95% CI)	P value	N	PPP: N (%)	OR (95% CI)	Adjusted OR (95% CI)	P value
THA														
Non-Obese			1											
Obese			1											
TKA														
Non-Obese			1											
Obese			1											
Medial UKA														
Non-Obese			1											
Obese			1											

HEALTH RESEARCH ETHICS AND GENERAL CONSIDERATIONS

Funding

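### The adjusted model has no measure of pre-operative systemic illness, so the adjusted odds ratios, above all for weight losers, could be confounded by it

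*Combined protocol and SAP*

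**What the plan says.** The Statistical analysis section defines gainers, losers and maintainers by a 5% change in weight. It estimates odds ratios "amongst gainers and losers in relation to those who maintained their weight". On covariates it states: "We will run a non-adjusted analysis first, then we will adjust for age, sex and the use of cement". It adds "We will stratify for baseline obesity status", with a cut at BMI 30. Table 2 has an adjusted OR column for gainers and for losers.

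Two sensitivity analyses are planned. One compares morbid with non-morbid obesity. For the other, "we will run another sensitivity analysis adjusting for patients having other chronic pain condition"; this variable is a survey item (Questionnaire section).

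The variables to be described in Table 1 are "age, sex, BMI and surgical details (type of anaesthesia, operation length, use of local infiltration analgesia (LIA), use of cement, and surgical complications"). There is no comorbidity index, physical-status class or diagnosis history. The listed questionnaire items do not ask why weight changed, and no exclusion for serious illness is stated.

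On sources, the Sample characteristics section identifies patients by diagnosis and procedure code from the "Danish National Patient Register by using SKS-code". Baseline characteristics "will be gathered from the Danish Hip Arthroplasty Register (DHR) and the Danish Knee Arthroplasty Register (DKR").

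**The concern.** The exposure is observed weight change over roughly a year, so deliberate loss and loss driven by illness fall into one category. Illness that precedes surgery, such as cancer or heart or lung disease, can plausibly lead to a 5% loss (or to a gain) and can also raise a pain score. That makes it a confounder that precedes the exposure. Age and sex carry part of it; use of cement is an implant choice and was not selected to represent illness.

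The Introduction gives the aim as finding factors that could help prevent persistent postoperative pain (PPP). A reader of Table 2 will take the adjusted OR as the answer after confounding has been dealt with. If losers are sicker than maintainers, a modest benefit of weight loss could be reported as no association. With no comorbidity row in Table 1, the imbalance would not be visible either.

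**Working it through.** **The plan's own figures.** The plan gives none for comorbidity or confounding. Its sample size reproduces: 6400 × 0.70 / 2 = 2240 per joint group, of whom 15%, or 336, are expected gainers. No share is given for losers, so the power statement neither supports nor weakens this point.

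**Inputs, all assumed.** Illness prevalence in maintainers p = 0.25; PPP without illness b = 0.18; illness-weight-loss OR (ORx) 1.8-2.5; illness-PPP OR (ORy) 1.6-2.5; true loser OR 1.00.

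**Formulas.**
- Illness prevalence in losers: pL = p·ORx / (1 − p + p·ORx).
- PPP with illness: odds = ORy × b/(1 − b), converted to a risk r.
- PPP in losers: pL·r + (1 − pL)·b. PPP in maintainers: p·r + (1 − p)·b.
- Apparent OR: ratio of the two odds.

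**Lower case (ORx 1.8, ORy 1.6).**
- pL = 0.45/1.20 = 0.375.
- Odds 0.2195 × 1.6 = 0.351, so r = 0.260.
- Losers: 0.375 × 0.260 + 0.625 × 0.18 = 21.0%. Maintainers: 0.25 × 0.260 + 0.75 × 0.18 = 20.0%.
- Apparent OR = (0.210/0.790)/(0.200/0.800) = 1.06.

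**Upper case (ORx = ORy = 2.5).**
- pL = 0.625/1.375 = 0.4545.
- Odds 0.2195 × 2.5 = 0.549, so r = 0.354.
- Losers 25.9%, maintainers 22.4%; apparent OR 1.22.

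**True OR 0.80** (loser odds multiplied by 0.80 at each illness level).
- Lower case: losers 17.6% against 20.0%, apparent OR 0.85.
- Upper case: losers 22.0% against 22.4%, apparent OR 0.98.

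**Wider range.** With p 0.15-0.35, both component ORs 1.5-3 and b = 0.18, a true OR of 1.00 appears as 1.03 (p 0.15, both ORs 1.5: 19.4% v 19.0%) up to 1.33 (p 0.30, both ORs 3: 30.2% v 24.5%). If ORy stops at 2.5, the top is 1.27.

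**The direction is conditional.** If illness were less common in losers (ORx = 1/1.8, ORy 1.6), pL = 0.139/0.889 = 0.156, losers have 19.2% against 20.0%, and the apparent OR is 0.95.

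**Room in the model.** Table 2 has six joint-by-obesity strata. Each model has 5 parameters besides the intercept: two weight terms and three covariates. In an assumed stratum of 200-400 patients with PPP of 10-20% there are 20-80 events, or 4-16 per parameter. One added term gives 20/6 = 3.3 to 80/6 = 13.3. This argues for a single index over a list of diseases.

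**The case against.** The plan is not silent on comorbidity. Adjusting for another chronic pain condition is directly relevant to a pain outcome, so it would be wrong to say that no analysis touches the subject. That stands. But the adjustment sits outside the main model, is reported after the weight change, and does not capture systemic illness.

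Age, sex and obesity stratification may already remove part of the confounding. This also stands, and the figures above are gross of it.

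The stated objective is association, and a stated limitation would meet some of the concern. But the plan itself chose to present adjusted ORs and names prevention as the purpose.

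On feasibility, the patient register's only stated use is selecting patients. The Ethics section mentions contact information and linkage to perioperative data, not diagnosis history, and the key for linking to that register is not spelled out. Permission for a look-back therefore cannot be assumed.

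A reader might infer more than the documents support in three ways:
- **That the loser OR is biased toward harm.** This requires illness to be more common in losers than in maintainers, which the documents do not show. Illness can also accompany gain, so the gainer contrast may be affected in either direction.
- **That a protective association would be reversed.** Stronger assumptions can do this: with PPP of 15% without illness, an illness-PPP OR of 3 and illness in 40% of losers against 10% of maintainers, a true 0.80 appears as 1.17. But those prevalences imply an illness-weight-loss OR of (0.4/0.6)/(0.1/0.9) = 6, and nothing in the documents points there.
- **That every recorded surgical variable belongs in the model.** Anaesthesia type and operation length precede the weight change, but no link from them to weight change is given, so they have not been shown to be confounders.

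**Conclusion.** The point holds as a possible, unmeasured confounding of the adjusted ORs, chiefly for losers. It is worth correcting but does not invalidate the study. The omission itself is certain from the text; the direction and size are not. Under the central assumptions a null loser OR would appear as 1.06-1.22, and 1.03-1.33 over the wider set. A true 0.80 would be diluted to about 0.85-0.98, so a modest protective association could be hidden. All of these rest on assumed prevalences and ORs and on a single binary confounder.

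**What to change.** 1. Subject to data permission, extend the National Patient Register extract to hospital diagnoses in a fixed look-back before the index operation (for example 5 years). Confirm and state in the plan that the permission and linkage cover this.
2. Derive one summary comorbidity index from pre-operative diagnoses only, so that consequences of weight change are not adjusted away. Add it to the adjusted model and as a row in Table 1.
3. Add one sensitivity analysis of the loser contrast that excludes patients with a new serious diagnosis (for example cancer) between surgery and survey, since a pre-operative index misses illness that arises later.
4. State that the intention behind weight loss remains unknown, because hospital diagnoses cannot supply it.

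If permission is refused, name the missing comorbidity adjustment as a limitation beside the adjusted ORs.

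Cost: a wider data request or a permission update, and slightly wider confidence intervals in the small strata. No extra patients or questionnaire items are needed.

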Weight change and the risk of chronic pain following hip and knee arthroplasties: A nationwide registry-based cohort survey study.

Authors/Collaborators:

[name]^{1,2,3}, MD, PhD Fellow; [name]^{1,3}, MD, PhD Fellow; [name], PhD, Associate professor⁴; [name], DMSc, Professor^{1,3}

Affiliations:

1. Department of Orthopaedic Surgery and Traumatology, Copenhagen University Hospital, Bispebjerg and Frederiksberg, Copenhagen, Denmark; 2. The Parker Institute, Copenhagen University Hospital, Bispebjerg and Frederiksberg, Copenhagen, Denmark; 3. University of Copenhagen, Department of Clinical Medicine, Faculty of Health and Medical Sciences; 4. Department of Orthopaedic Surgery and Traumatology, Odense Hospital, Odense, Denmark.

INTRODUCTION

The treatment of hip and knee osteoarthritis not responding to non-surgical treatments may be surgical joint arthroplasty.¹ Though arthroplasty is considered an effective and safe treatment, unfavourable outcomes have been reported,² including persistent postoperative pain (PPP). The association between body weight and outcomes following total hip arthroplasty (THA) and knee arthroplasty is well documented: overweight carries higher risk of bad functional and surgical outcomes.³⁻⁹ Also, Preoperative weight reduction reduces general health related complications following knee arthroplasty.¹⁰ However, only few studies have investigated weight change following THA and knee arthroplasty.¹¹⁻¹⁶ Of these, some have indicated that weight change influences postsurgical outcomes.

Identification of factors that are linked to the incidence of PPP could help us to prevent this problematic outcome. The objective of this study is to investigate whether weight change is associated with the incidence of PPP following THA and knee arthroplasty across non-obese and obese patients.

METHODS

Study design

The study is a nationwide, register-based cohort survey study. We will report the results following the CROSS checklist for standardized reporting of survey studies.¹⁷ We will investigate the change of BMI 11-15 months after THA and knee arthroplasty and incidence of PPP by combining data from national registries and surveys.

Questionnaire

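### PPP is one last-week pain score taken in the same questionnaire as follow-up weight, with no earlier pain score planned, so the labels incidence and risk of developing PPP claim more than the design can show

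*Combined protocol and SAP*

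**What the plan says.** **Outcome.** Under Questionnaire, pain is "a numerical rating scale (NRS) question for pain in the operated joint in the last week". Under Statistical analysis, the primary outcome is PPP, defined as an NRS score above 3. No onset, duration or change-from-baseline criterion is attached.

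**Exposure.** Follow-up weight comes from the same form, whose last listed items are "patient-reported use of analgesics; weight; height and the permission to contact respondents again later". The starting point is pre-operative: under Sample characteristics, "The baseline characteristics of the sample including their BMI will be gathered from the Danish Hip Arthroplasty Register (DHR" and its knee counterpart. Gainers and losers are defined by a change of at least 5%.

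**Timing.** Patients are those who "received their arthroplasty 11-15 months prior to the intended date of survey administration". The survey is answered once; under Survey administration, reminders go to non-responders only.

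**Labels.** Study design announces an investigation of "the change of BMI 11-15 months after THA and knee arthroplasty and incidence of PPP". The objective and the sample-size text also use the word incidence, the title speaks of risk, and the primary table is headed "Table 2 (Risk of developing PPP". The Introduction gives the motive: "Identification of factors that are linked to the incidence of PPP could help us to prevent this problematic outcome".

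**The concern.** A single assessment of pain yields a prevalence (strictly, over a one-week recall period). To speak of patients developing PPP, one needs to know their pain state earlier, and the plan collects no such information. All patients were operated on for osteoarthritis, so an NRS above 3 at a year may be pain that arose after surgery or pain that never went away.

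The second difficulty is direction. Weight may have changed before, during or after the period in which pain became established. Patients whose joint still hurts may move less and gain weight; patients who gain weight may come to have more pain. The planned comparison cannot separate these, and the document nowhere discusses temporal order or reverse causation.

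At stake is how the primary result will be read. A significant odds ratio under the present table heading, in a paper whose stated motive is prevention, invites the conclusion that avoiding weight gain would prevent PPP.

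**Working it through.** **1. Is an earlier pain score planned anywhere?**
- Questionnaire: "A 22-question questionnaire will be sent to the eligible candidates". The listed content is WOMAC pain 5, DN4i 7, NRS 1, satisfaction 1, and eight single items (willingness, pain frequency, interference, other chronic pain, analgesics, weight, height, permission to re-contact). 5 + 7 + 1 + 1 + 8 = 22, so no item is left for pre-operative pain or pain onset.
- Baseline variables (Statistical analysis, Table 1): age, sex, BMI and surgical details. No pain score.
- Adjustment: age, sex and cement. No pain score.
- Sensitivity analysis: other chronic pain conditions, reported in the same follow-up questionnaire. This concerns pain elsewhere and does not date the joint pain relative to the weight change.

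**2. Plan figures used.** 6400 × 0.70 / 2 = 2240 per joint, as stated. With 15% gainers: 0.15 × 2240 = 336 gainers and 1904 non-gainers. The plan's detectable difference of 16.6% is not used here.

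**3. Two opposite mechanisms, one table.** Assumed rates, not from the documents:
- Weight acts on pain: PPP 20% in non-gainers and 27.3% in gainers (OR 1.5). Cells per 2240: gain and PPP 91.6; gain, no PPP 244.4; no gain, PPP 380.8; neither 1523.2.
- Pain acts on weight: gain in 91.6 / (91.6 + 380.8) = 19.4% of those with PPP and 244.4 / (244.4 + 1523.2) = 13.8% of those without. These are the same four cells, with the same OR of 1.5.

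**4. Illustration with no effect of weight on pain.** Assume PPP 20%, a pain-to-gain OR of 1.5 and 15% gainers overall. Solving gives gain in 19.5% with PPP and 13.9% without (0.20 × 0.195 + 0.80 × 0.139 = 0.150).
- PPP in gainers = 0.20 × 0.195 / 0.15 = 26.0%.
- PPP in non-gainers = 0.20 × 0.805 / 0.85 = 18.9%.
- Two-sided 5% test, 336 v 1904: difference 0.070; standard error under the null √[0.20 × 0.80 × (1/336 + 1/1904)] = 0.0237; under the alternative 0.0255. Power = Φ[(0.070 − 1.96 × 0.0237) / 0.0255] = 0.82.
- Sensitivity to the assumptions: 0.62 at 10% PPP and 0.90 at 30%. At 20% PPP, 0.47 for a pain-to-gain OR of 1.3 and above 0.99 for 2.0.

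**5. The comparison Table 2 actually makes.** It sets gainers against maintainers, by procedure and obesity status, in six rows. Row sizes are not given. Assume 15% losers (so 70% maintainers) and PPP in maintainers equal to the 18.9% in non-gainers:

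| Assumed row size | Gainers v maintainers | Power |
|---|---|---|
| 1344 | 202 v 941 | 0.61 |
| 1120 | 168 v 784 | 0.54 |
| 896 | 134 v 627 | 0.46 |
| 448 | 67 v 314 | 0.27 |

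**The case against.** **The objective speaks of association.** It does, and the outcome is also called an occurrence. The plan contains no conclusion text and no causal estimand. A reader might infer that the study is set to report that weight gain raises the risk of PPP; the documents do not say so. What stands is that the objective is association with incidence, and that the table heading goes further.

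**Incidence can be a convention.** Persistent post-operative pain cannot exist before surgery, so one may call the proportion affected at a fixed interval an incidence, and unresolved pain still counts as persistent. That is a fair defence of the one word. It does not rescue the wording about developing PPP, and it does not settle whether pain or weight change came first.

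**This is a cohort.** A reader might call the association purely cross-sectional. That would be wrong: the exposure is a change from pre-operative register BMI in patients defined by operation date. Only the end of the exposure window coincides with the outcome. The order of events within the 11-15 months is still unobserved.

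**The odds ratio is symmetric in any 2×2 table.** True, including in a prospective study with clear time order, so symmetry is no evidence of a defect. The defect is that nothing else in this design supplies the order.

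**The rates are assumed.** Also true. They show that reverse causation is possible at a visible size, not that it is likely.

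**Conclusion.** The point holds: the labels are wrong as written. One questionnaire supplies both the outcome and the end of the exposure, and no earlier pain score is planned, so the study can estimate the prevalence of NRS above 3 at 11-15 months by weight-change category. It cannot identify new onset or direction. The planned estimates themselves are unaffected; what changes is what may be concluded from them.

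The size is illustrative only. It rests on 2240 per joint and 15% gainers (both from the plan) and on 20% PPP and a pain-to-gain odds ratio of 1.5 (both assumed). On those terms, 26% v 19% PPP would appear with no effect of weight on pain, and would be significant with power of about 0.82 for gainers v non-gainers in a whole joint. It would be wrong to carry 0.82 over to Table 2: its rows are smaller and compare gainers with maintainers, where power is about 0.27 to 0.61 under the assumed row sizes. Nor do the documents show that the registers lack pre-operative pain scores; they show only that none is planned for use.

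**What to change.** - Define the primary outcome as the prevalence of NRS above 3 at 11-15 months.
- Retitle Table 2: *Association between weight-change category and prevalence of PPP at 11-15 months*.
- Replace the incidence and risk wording consistently in the title, objective, Study design, sample-size text and tables.
- State in advance that conclusions are limited to an association between weight change since surgery and concurrent pain, of undetermined direction, with no claim that avoiding weight gain prevents PPP.

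This needs no new data and leaves the models unchanged. The only cost is a more modest conclusion. If a source of pre-operative pain scores exists, adjusting for them would be a useful addition, but it would not by itself settle direction and does not replace the changes above.
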